12.0 Statistical Analysis

Baseline characteristics will be summarized for patients who are randomized to the two treatments (HS vs. LS) at baseline. A crossover design eliminates confounding due to uneven distribution of baseline variables because a patient serves as his/her own control, thus a complete balance in baseline data is obtained in the absence of dropouts.

The outcomes of interest are the comparison of the change in blood pressure, vascular stiffness (Aix, PWV), endothelial function (PAT), insulin resistance (HOMA), skin Na^+ concentrations, and inflammation (DAS28 score) between baseline and 1) after 8 weeks of HS diet, 2) after 8 weeks of LS diet. We will use Analysis of Covariance (ANCOVA) which is a form of multiple linear regression model including the blood pressure at the end of each treatment (HS and LS) or the last observation for patients with early withdrawal as an outcome variable, group variable (HS or LS) as a main independent variable, and baseline blood pressure as a covariate. By including the baseline value as a covariate, the regression coefficient for the group (HS or LS) becomes the between-group (HS vs LS) difference in the change in blood pressure response. This method is often superior to the method that used the change in blood pressure directly as the outcome variable (such as student's t-test for the change) because it adjusts for baseline differences as a covariate which reduces measurement errors more effectively.

A similar approach will be used for the vascular stiffness (Aix, PWV), endothelial function (PAT), insulin resistance (HOMA), and inflammation (DAS28 score) and skin Na^+ concentrations.

If unequal distribution of some of the variables is detected by the univariate analyses of baseline characteristics between groups, those variable will be included in a multiple linear-regression model in addition to a set of a prior chosen covariates based on clinical relevance such as age, sex, and race, with knowledge of not overfitting the model

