High-salt intake adversely affects endothelial function and leads to vascular stiffness^{7,8,11}. To determine the effects of high-salt intake on endothelial function and vascular stiffness in RA, we will measure augmentation index (AiX) and pulse wave velocity (PWV) at each visit. Subjects will undergo non-invasive pulse-wave analysis using the commercially available SphygmoCor system (AtCor Medical, Sydney, Australia). This system uses a transfer function to calculate central arterial pressure from measurements obtained at the radial artery by a hand-held tonometer (Millar pressure tonometer, PWV Medical, Sydney, Australia). After at least 10 minutes of supine rest, peripheral blood pressure will be measured twice using an automated sphygmomanometer (Dinamap Pro 110, GE Healthcare, WI, USA) and augmentation index, aortic (carotid to femoral) pulse-wave velocity (PWV) and brachial (carotid to radial) PWV will be determined using applanation tonometry. The tonometer will be held at the point of maximal pulsation and pressed lightly against each respective artery (i.e., radial, carotid, and femoral arteries.) Measurements are recorded after at least 12 consecutive beats, and the quality of the waveforms confirmed by the quality control function provided by the software. Since augmentation index is influenced by heart rate, an index normalized for a heart rate of 75 beats per minute is used.

Endothelial function will be measured using peripheral arterial tonometry (PAT), a finger plethysmographic device allowing isolated detection of pulsatile arterial volume changes will also be used to assess endothelial function in relation to the salt diet. This device (Itamar Medical Ltd., Caesarea, Israel) consists of two finger-mounted probes, which include a system of inflatable latex

air-cushions within a rigid external case. The probe design allows the application of a constant and evenly distributed near-diastolic counterpressure within the entire probe, which increases sensitivity by unloading arterial wall tension, and prevents venous blood pooling to avoid venoarteriolar reflex vasoconstriction. Pulsatile volume changes of the fingertip are sensed by a pressure transducer and transferred to a personal computer where the signal is processed and stored. The change in flow post-occlusion reflects endothelial function.

5. MRI measurement of tissue Na⁺ content (visits 2 and 4)

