Each subject will have two MRIs. These will be performed at the end of the low-salt and high-salt phases. We will quantify Na⁺ content in skin and muscle by ²³Na MRI using a 3.0 T Phillips Achieva scanner, equipped with a ²³Na coil. Scans will be performed in the Vanderbilt University Institute of Imaging Science. This will take about an hour. Urine pregnancy testing will be performed before the MRI in women of childbearing potential. The MRI will be scheduled on the same days as visits 2 and 4 if possible; however, it is possible that for logistic reasons this may not always be possible and the MRI and in that case the MRI and clinical visits will occur on different days.

6. Microbiome specimen collection (all visits)

Stool and oral microbiota samples will be obtained from participants at each study visit. Microbiota specimens will be used to examine the relationship between microbiota and disease characteristics as well as responses to salt and will be stored for future studies.

Stool collection: Stool from a single bowel movement will be collected by the subject before each study visit. Subjects will be provided with instructions and a materials kit for collecting stool prior to the study visit. Subjects will bring collected stool to the study visit. Stool will be collected within 24 hours before the study visit and will be kept at room temperature.

Oral microbiota collection: Subjects will be asked to not brush or floss teeth within 12 hours of the scheduled assessment. Subjects will be asked to spit into a sterile container. Approximately 5 ml of saliva will be collected and frozen at each study visit.

Table 1.A Procedures and Labs - Study Summary

Procedure/Lab	Screen, virtual* *	Screen, in person	Visit 1 Baseline #1	Visit 2 HS/LS	Visit 3 Baseline #2	Visit 4 HS/LS
History	+		+	+	+	+
Exam		+	+	+	+	+

Joint Count	Self report	+	+	+	+	+
Disease activity			+	+	+	+
Aug Index			+	+	+	+
PWV			+	+	+	+
PAT			+	+	+	+
24-hr Blood pressure			+	+	+	+
Na+ MRI				+		+
CBC		+*				
ALT, AST, creatinine		+*				
Insulin			+	+	+	+
Glucose			+	+	+	+
hsCRP			+	+	+	+
ESR			+	+	+	+
Plasma			+	+	+	+
Serum			+	+	+	+
24-hr Urine			+	+	+	+
DNA/RNA			+			
Stool			+	+	+	+
Saliva			+	+	+	+
Pregnancy testing, urine		+	+	+	+	+

*Labs only drawn at in-person screening if not available from previous 12 weeks.

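### The main analysis is not settled: Section 10 promises mixed models on change, Section 12 writes an ANCOVA with no patient or period term, and skin sodium has no baseline scan for either

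*Combined protocol and SAP*

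**What the plan says.** **Section 10 (Sample Size)** sizes the trial with a paired t-test on post-treatment values, two-sided 5%, n=18. It claims 95% power for a 1.0-unit DAS28 difference and about 98% for a 5 mmol/L skin Na+ difference with an SD of about 5.0. It then says the real analysis will compare change from baseline between phases with linear mixed models, that this will raise power, and that the paired sizing is therefore the most cautious case. It lists no model terms.

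**Section 11** names ANCOVA with last observation carried forward.

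**Section 12** says "We will use Analysis of Covariance (ANCOVA) which is a form of multiple linear regression model". The outcome is the end-of-diet value "or the last observation for patients with early withdrawal as an outcome variable", with "group variable (HS or LS) as a main independent variable, and baseline blood pressure as a covariate". The only additions allowed are imbalanced baseline variables and covariates such as age, sex and race. The same section relies on the fact that "a patient serves as his/her own control".

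Section 12 also puts skin Na+ among the change outcomes ("The outcomes of interest are the comparison of the change in blood pressure, vascular stiffness (Aix, PWV), endothelial function (PAT), insulin resistance (HOMA), skin" Na+ and DAS28) and extends the ANCOVA to it: "A similar approach will be used for the vascular stiffness (Aix, PWV), endothelial function (PAT), insulin resistance (HOMA), and inflammation (DAS28 score) and skin" Na+. But Section 6.0 states: "Each subject will have two MRIs. These will be performed at the end of the low-salt and high-salt phases". Table 1.A agrees, with sodium MRI at Visits 2 and 4 only.

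**The concern.** There are three faults.

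1. Two different main analyses are named. Section 10 promises a comparison of change. Section 12 argues that ANCOVA is often better than using change as the outcome.
2. The only model written out does not match the design. Each completer contributes two correlated rows, but there is no patient term and no period term. Section 12 also does not say whether baseline is Visit 1 for both rows or each period's own (Visits 1 and 3).
3. For skin Na+ there is no baseline value in either period, so neither the Section 10 comparison nor the Section 12 ANCOVA can be run.

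The analyst would have to choose among models with different standard errors after the data are in, in a trial where patients know their diet and many outcomes are tested. For one of the two sizing outcomes, no analysis section states a feasible analysis.

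**Working it through.** **Inputs from the documents.** n=18 completers; two-sided 5%; skin Na+ difference 5 and SD about 5.0 (type of SD not stated); DAS28 difference 1.0 with no SD. **Assumed:** all correlations, because the documents give none.

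**The plan's own figures.** Paired t power uses a noncentral t with 17 df and noncentrality (difference / SD of difference) × √18.
- Skin Na+: 5/5 = 1 gives 97.9%, matching the stated 98%. This holds if 5.0 is the SD of the difference, or if it is the per-visit SD s with correlation ρ = 0.5, since SD of difference = s√(2(1−ρ)) = 5.
- DAS28: 95% requires 1.0/SD = 0.9025, so the SD of the difference is 1.108.

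**Skin Na+ under the Section 12 model.** Without a baseline only diet remains, which is an unpaired comparison of 18 against 18 values. Its standard error targets √(2s²/18), while the true value is √(2(1−ρ)s²/18). The ratio is about 1/√(1−ρ). Simulation gives:

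| ρ | Unpaired power, per-visit SD 5 | Paired power, per-visit SD 5 | SE / true SD | Type I error | Unpaired power, SD of difference 5 |
|---|---|---|---|---|---|
| 0.3 | 87% | 92% | 1.19 | 2.1% | 96% |
| 0.5 | 90% | 98% | 1.40 | 0.8% | 90% |
| 0.7 | 94% | 99.9% | 1.80 | 0.1% | 70% |
| 0.8 | 96% | 100% | 2.21 | 0.02% | about 41% |

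In the last column paired power is 97.9% throughout. Its two lowest rows need per-visit SDs of 6.5 and 7.9, from 5/√(2(1−ρ)).

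**DAS28 under the Section 12 model.** Simulation, 9 per sequence, SD of difference 1.108 (95% paired).
- Equal correlation among the four visits, 0.3/0.5/0.7/0.8: own-period baseline 92/87/82/80%; Visit 1 baseline for both rows 93/90/87/86%. Type I error is about 3% to 4% and 1% to 3% respectively.
- Own-period baseline, within-period/across-period correlation 0.6/0.5: 92%. At 0.7/0.5: 96%, so no loss.

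**Does analysing change raise power?** Let w be the within-period and a the across-period correlation.
- Variance of the difference in changes: 4(1−w)s².
- Variance of the difference in end values: 2(1−a)s².
- Change wins only if w > (1+a)/2, that is above 0.65, 0.75 and 0.85 for a = 0.3, 0.5 and 0.7.
- For DAS28 with w = a, the SD is 1.108 × √2 = 1.567 and power is 72%. At w/a = 0.6/0.5, 0.7/0.5 and 0.8/0.5 it is 81%, 91% and 98%.

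**Period.** With 12:6 sequences and no period term, an end-value comparison is biased by (12/18 − 6/18) = 1/3 of any period shift.
- An assumed 0.5-unit DAS28 drop gives 0.5/3 = 0.17 if it appears only at Visit 4. With own-period baseline ANCOVA under equal correlation it gives 0.03 to 0.11 if already present at Visit 3.
- At 9:9 there is no bias, but an unmodelled 0.5 drop lowers paired power from 95% to 92%.
- No blocking is stated. Under simple randomisation (assumed), Binomial(18, 0.5) gives 11:7 or worse with probability 48% and 12:6 or worse with probability 24%.

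**The case against.** The best defence is that the texts can be combined. Section 12 says the diet coefficient, with baseline in the model, estimates the difference in change, so a mixed model with baseline as a covariate would satisfy both sections, and a mixed model for two phases in one patient normally has a random patient effect. Section 11's ANCOVA sits under dropouts and may be meant as a sensitivity analysis. Tables 1.A and 1.B label Visits 1 and 3 as first and second baselines, which points to own-period baselines. The paired t-test in Section 10 is feasible for skin Na+. Finally, every power loss depends on an assumed correlation.

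Much of this is fair. The combined reading is reasonable, but Section 12 describes a multiple linear regression and lists its terms, and no section writes a patient or period term. The table labels make own-period baselines the likelier intent without Section 12 saying so. The Section 11 reading does not help, because Section 12 gives ANCOVA as the analysis anyway. The paired t-test for skin Na+ is used for sizing, and the next sentence replaces it. No reading supplies a baseline scan. The figures show that Section 10's power claim is not assured; they do not show that the trial is underpowered.

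**Conclusion.** The concern holds and should be fixed. The conflict between sections, the missing patient and period terms and the missing baseline scan follow from the text and need no assumption.

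The statistical harm is moderate. Read literally, Section 12 does not inflate type I error when no period effect is present; it is conservative and can lose power. The loss for skin Na+ is about 4 to 8 points with a per-visit SD of 5, larger at high correlation if 5.0 is the SD of the difference. For DAS28 it ranges from none to about 15 points. Bias from omitting period needs unequal sequences among the analysed patients and, for the assumed 0.5-unit DAS28 drop, is small against 1.0. Section 10's statement that its analysis must beat the paired test is true only under correlations the plan does not give. The sample size of 18 is not undermined.

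**What to change.** Name one primary analysis and use it consistently in Sections 10, 11 and 12: a linear mixed model on the end-of-diet value with fixed diet and period, a random patient effect and small-sample degrees of freedom.

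- **Skin Na+:** apply this model to the two end-of-diet scans with no baseline, and remove skin Na+ from the change-from-baseline wording. With complete data the model has 16 df and 97.8% power at the planning values.
- **Outcomes with baselines:** state whether the period's own baseline (Visit 1 or 3) enters, and how. Two choices are acceptable if one is fixed in advance: no baseline (about 95% for DAS28), or the patient's mean baseline plus the period's deviation from it (93% under equal correlation, 96% at 0.7/0.5).
- **Section 11:** say whether the ANCOVA with last observation carried forward is a sensitivity analysis.
- **Section 10:** delete the claim that the paired sizing is the most cautious case, or state the correlation under which it holds.

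The cost is wording, on the same data and the same n=18. Period takes one degree of freedom (17 to 16): 97.9% to 97.8% for skin Na+ and 95.0% to about 94.9% for DAS28, plus any for baseline terms.

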5.0 Methods

Subjects and recruitment: Patients with RA will be recruited from the rheumatology clinics of the Vanderbilt University Medical Center, by word of mouth from the practices of physicians of the Vanderbilt Rheumatology Practice, from the private practices of community rheumatologists, and by advertising. MyHealth@Vanderbilt and other VUMC-based advertising methods may be utilized. Inclusion criteria will be used to search eStar for

potential participants. Once identified, we will contact the patient's physician to ask for an introduction, with the patient's permission.

a. Inclusion criteria

1. Male and female patients older than 18 years who are willing to participate.
2. Satisfy the ACR criteria for the diagnosis of RA.
3. Have stable disease activity as evidenced by no clinically meaningful change in immunomodulating or corticosteroid therapy in the past 1 month.
4. Have moderate disease activity as reflected by a minimum of 3 swollen and tender joints.

b. Exclusion criteria

1. Pregnancy
2. Receiving dialysis
3. Organ or bone marrow transplant
4. Taking diuretics, uncontrolled hypertension ($>160/100$ mmHg), or cardiac failure requiring treatment.
5. Severe edema (as judged by the investigator)
6. Diabetes mellitus treated with an insulin pump
7. Major surgery within the previous 3 months
8. Severe co-morbid conditions such as active cancer likely to compromise study participation
9. Unwillingness, or other inability, to cooperate
10. Contraindication to MRI
11. Presence of a condition that could make 24-hour blood pressure monitoring difficult: atrial fibrillation, inability to operate machine, receiving anticoagulants, presence of a condition that in the opinion of the investigator may be exacerbated by blood pressure cuff inflation (e.g., lymphedema).

c. Screening, randomization, and blinding

Patients will be screened for eligibility and those who wish to participate and provide informed consent will enter the study.

d. Design

This will be a random-order, 2-period crossover study with washout.

e. Concomitant therapy

Patients will continue to receive their regular therapy for RA. If a patient's disease flares and requires a significant change in therapy, the subject will be withdrawn from the study, and we will have the patient return for an exit visit.

[figure not shown]
f. Dietary regimen

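### Section 12.0 lets baseline comparisons choose covariates in a pooled ANCOVA that names no patient or period term; the trigger itself changes little, but its covariates do not replace the patient term

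*Combined protocol and SAP*

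**What the plan says.** Section 5.0 sets the design: "This will be a random-order, 2-period crossover study with washout". The regression in Section 12.0 takes the value at the end of each diet as outcome, diet group as the main predictor and the baseline value as covariate. It names no patient, period or sequence term.

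On baseline variables, Section 12.0 states "A crossover design eliminates confounding due to uneven distribution of baseline variables because a patient serves as his/her own control", and limits this at once: "thus a complete balance in baseline data is obtained in the absence of dropouts". It ends with the trigger, "If unequal distribution of some of the variables is detected by the univariate analyses of baseline characteristics between groups". Variables so detected enter the model "in addition to a set of a prior chosen covariates based on clinical relevance such as age, sex, and race", restrained only by "with knowledge of not overfitting the model". There is no list of variables to compare, no threshold, no cap and no closed covariate list. It does not define the groups, though its opening sentence, "Baseline characteristics will be summarized for patients who are randomized to the two treatments (HS vs. LS) at baseline", suggests the groups formed by first-period diet.

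Two other sections bear on this. Section 10.0 sizes the trial at 18 with a paired t-test and says that the actual analysis will use linear mixed effect models. Section 11.0 recognises that dropout between phases can confound, plans a balance check for that reason, and again names ANCOVA, with the last observation carried forward.

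**The concern.** The trigger has no sound target under either reading of the groups. If they are the HS and LS phases, age, sex, race and every other fixed characteristic are the same in both for patients who complete both, so there is nothing to detect. If they are the first-period groups, randomization makes any difference a chance one, and fixed patient characteristics cancel from a within-patient contrast anyway. Either way the final model is settled only after the data are seen.

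What is at stake is mainly efficiency and clarity. The sample size rests on a paired comparison, while the regression described does not use the pairing. Patient-level covariates look like a partial remedy, so the question is whether they recover what a patient term would give. A reader also cannot tell which model will produce the reported result for each outcome.

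**Working it through.** **The plan's own figure.** Section 10.0 gives about 98% power for skin Na⁺ with n = 18, difference 5 mmol/L, SD 5.0 mmol/L, two-sided 5%. Taking 5.0 as the SD of the paired difference, the noncentrality is (5/5.0) × √18 = 4.24 on 17 df, and power is 97.9%. The figure is reproduced, but as the power of a paired analysis.

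**How often the trigger fires.** The plan gives neither the number of variables nor a threshold. Assume k independent variables, each tested at 5% between first-period groups. The chance of at least one hit is 1 − 0.95^k: 23% for k = 5, 40% for k = 10, 54% for k = 15, 64% for k = 20. Between the HS and LS phases of completers it is 0 for fixed characteristics.

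**What firing does to the result.** Simulations used 18 completers, 10 variables of which one was prognostic, and the pooled ANCOVA of Section 12.0.

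- Correlation 0.5 or 0.7, effect 0, 0.6 or 1 SD, 4,000 runs each: the trigger fired in about 40% of runs. When it did, the diet estimate moved by a median of under 0.01 standard error (95th percentile at most 0.08). Significance changed in 0.1% to 0.8% of all runs.
- A separate set of 2,000 runs (patient variance 0.6, residual variance 0.4, prognostic coefficient 0.4): type I error was 2.9% without and 3.0% with the trigger, and the SD of the estimate was 0.253 both ways. Both error rates are below 5% because the pooled model ignores the pairing.
- Random dropout in that second set: rejection under no effect was 4.0% both ways with 4 of 22 lost, and 5.2% without against 4.8% with the trigger when 32 of 50 were lost.

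**What omitting the patient term does.** Take total SD 1 and equal correlation ρ among a patient's measurements. Adjusting for baseline leaves residual variance 1 − ρ²; a patient term leaves 1 − ρ. With 18 per diet, the standard error of the diet effect is √(2 × variance / 18).

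- ρ = 0.5: pooled √(2 × 0.75/18) = 0.289; within-patient √(2 × 0.50/18) = 0.236. For an effect of 0.6 the ratios are 2.08 and 2.55.
- ρ = 0.7: pooled √(2 × 0.51/18) = 0.238; within-patient √(2 × 0.30/18) = 0.183. The ratios are 2.52 and 3.29.

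The noncentral t on 16 df gives 67% and 87% for the two within-patient ratios, in line with the simulation (18 completers, effect 0.6 SD, 4,000 runs):

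| Model | ρ = 0.5 | ρ = 0.7 |
|---|---|---|
| Pooled ANCOVA | 53% | 69% |
| Pooled, trigger applied | 53% | 69% |
| Pooled, three fixed covariates | 55% | 70% |
| Patient and period | 68% | 87% |
| Patient, period and period baseline | 64% | 85% |

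At an effect of 1 SD and ρ = 0.5, power is about 94% pooled against 98% with patient and period terms.

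**The case against.** The strongest reply is dropout. Section 12.0 claims complete balance only without it, Section 10.0 plans to enroll 50 because many may leave, and Section 11.0 says that losing patients between phases can confound. On that view the trigger is a contingency for incomplete pairs. This stands in part: HS and LS hold the same patients only among completers, and informative dropout could make adjustment useful. But the trigger is not confined to dropout, and comparisons in about 18 patients are a weak way to find a damaging imbalance. A patient term protects the contrast better. It must, however, be a random effect: with 32 of 50 lost, an analysis of complete pairs alone gave an SD of 0.223 for the diet effect, against 0.194 for the pooled model that keeps first-period data.

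Second, the numerical effect of the trigger is negligible with complete pairs. That stands.

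Third, Section 10.0 already names mixed models, which normally carry a patient term. So it cannot be said that the plan rules one out; the point is that Sections 11.0 and 12.0 describe something else and the sections need reconciling.

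Fourth, age, sex and race are chosen in advance and may help a little. In the second simulation set, at an assumed effect of 0.6, one pre-specified prognostic covariate raised pooled power from 57.8% to 59.6%. That stands too, and the plan nowhere offers these covariates as a substitute for a patient term.

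**Conclusion.** The point holds in limited form. The trigger makes the model data-dependent with no gain in precision, and should go. The material weakness is the pooled regression around it: about 15 points of power at correlation 0.5 (68 − 53) and 18 at correlation 0.7 (87 − 69), for an assumed 0.6 SD effect and 18 completers. At the 1 SD difference used for planning it is about 4 points (98 − 94, correlation 0.5). The correlations, the 0.6 SD effect, the 10 variables and the 5% threshold are assumptions; the documents give none of them for this purpose.

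A reader might infer that the reported estimate and p-value turn on which baseline comparisons happen to be significant, or that the 40% is a risk of a wrong conclusion. Neither is supported. The 40% is only how often the trigger would fire between first-period groups, and when it fires the diet estimate hardly moves. Nor does this point show a wrong sample size or an inflated type I error.

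**What to change.** In Section 12.0, delete the imbalance trigger. Pre-specify one model per outcome: diet and period as fixed effects, patient as a random effect so that incomplete pairs still contribute, plus the period baseline where it is measured. Skin Na⁺ has no period baseline, because Section 6.0 and Table 1.A place the MRI at visits 2 and 4 only; its model should say so. Align Sections 10.0, 11.0 and 12.0 on this model.

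Show baseline characteristics descriptively, without tests. Adjustment for age, sex and race may stay if the list is closed in advance; removing it is optional. Keep the dropout-balance check of Section 11.0 as a descriptive display.

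The cost is SAP wording and a few degrees of freedom, with no extra patients or data. Including the period baseline has a small price under the simulated conditions (68% to 64%, and 87% to 85%), so decide on it before the data are seen.
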